7.6. Tumor Biopsies for Mechanistic Exploratory Biomarkers

Tumor growth inhibition following treatment with 4-1BB agonist monoclonal antibodies or with PD-1 antagonist monoclonal antibodies has been associated with increases in tumor-infiltrating lymphocytes. Paired de novo tumor biopsies are mandatory for the patients enrolled in the expansion cohorts in order to determine whether the combination of PF-05082566 and MK-3475 has this effect. A de novo biopsy will be required at study entry followed by a second biopsy at the time of the Cycle 3 tumor assessment. For patients in dose escalation cohorts, unscheduled optional de novo tumor biopsies may be collected at the discretion of the Sponsor and Investigator to support the assessment of disease progression. Biomarkers that will be assayed may include but will not be limited to IHC assessment of tumor-infiltrating lymphocytes, PD-L1 IHC, quantitation of T cell receptor sequences, and gene expression.

Please refer to the Study Manual for details pertaining to specific days of sample collection, and sample preparation and shipping

CCI

7.8. Pharmacogenomic (RNA) Assessments

Blood samples for pharmacogenomic analysis will be required and will be collected on Day 1 of Cycles 1 and 2 (pre-dose). Samples will be used to explore gene expression signatures in PBMCs that would be predictive for or characteristic of responses to treatment. Candidate genes that might influence patient response, may include but will not be limited to CXCR3, IFNG, EOMES, CD28, ICOS, CD40LG, IL2RA, CD80, CCL5, FOXP3, CDC25A, GZMA, IL23A, SOCS1, IL10; PD-1, PD-L1.

7.9. Tumor Response Assessments

Tumor assessments will include all known or suspected disease sites. Imaging may include chest, abdomen and pelvis computed tomography (CT) or magnetic resonance imaging (MRI) scans; brain CT or MRI; bone scan and/or bone X-rays for patients with known or suspected bone metastases.

The same imaging technique used to characterize each identified and reported lesion at baseline will be employed in the following tumor assessments.

Antitumor activity will be assessed through radiological tumor assessments conducted at baseline, at Week 9, and every 6 weeks thereafter. Timing should follow calendar days and should not be adjusted for treatment delays. Follow up bone scans is required every 16 weeks only if bone metastases are present at baseline. Otherwise bone imaging is required only if new bone metastasis are suspected and at the time of confirmation of response for patients who have bone metastases. In addition, radiological tumor assessments will also be conducted whenever disease progression is suspected (eg, symptomatic deterioration), and at the time of End of Treatment (if not done in the previous 6 weeks). Note that a post-treatment biopsied lesion or a lesion that is radiated during the study should no longer count as a target lesion.

Assessment of response will be made using RECIST version 1.1 ([Appendix 1](#)). CCI

[REDACTED]

[REDACTED]

[REDACTED]

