32. **Follow Up:** Patients should be evaluated up to 90 days after last dose of study treatment. Refer to the protocol for specific guidelines. Patients continuing to experience toxicity following discontinuation of study treatment will continue to be followed at least every 4 weeks until resolution or determination, in the clinical judgment of the Investigator, that no further improvement is expected. PK and immunogenicity samples should be collected as described in the PK and Immunogenicity Assessment section in Schedule of Activities ([Table 3](#)). Patients whose disease has not progressed at the end of treatment will enter into disease follow-up. During this follow-up period, patients will have disease assessments performed every 12 weeks \pm 7-days. Once patients have exhibited disease progression or began a new anti-cancer therapy, or 6-month follow-up from the date of the first dose of the last enrolled patient, whichever occurs first, they will be withdrawn from the study. See [Section 4.3.1](#) Contraception for guidelines on contraception checks during this period.
33. **De novo tumor biopsy for biomarker assessment (Dose escalation):** For patients in dose-escalation cohorts, unscheduled optional de novo tumor biopsies may be collected at the discretion of the investigator and sponsor to support the assessment of disease progression.
34. **De novo tumor biopsy for biomarker assessment (Expansion cohorts):** Mandatory for patients in expansion cohorts only. A de novo biopsy will be required at study entry followed by a second biopsy at the time of the Week 9 scans (after 3 cycles of treatment).
35. **Continued Treatment Beyond Cycle 8:** This will be on a reduced visit schedule (Day 1 of each cycle), or as clinically indicated.
36. **Thyroid Function Tests:** To be collected every 2 cycles for the first 8 cycles, and then every 4 cycles (Cycles 1, 3, 5, 7, 11, 15 etc.).
37. **Hepatitis B and C Tests:** Conduct tests for hepatitis B surface antigen, core antibody, and anti-hepatitis C. Other tests may be conducted per standard practice to confirm an active hepatitis infection.

Table 4. Required Laboratory Tests

SAFETY LABORATORY REQUIREMENTS	
Refer to the Schedule of Activities table for specific timepoints and instructions	
Assessments	
Hematology Panel:	Chemistry Panel:
Absolute Neutrophil Count	Sodium
Hemoglobin	Potassium
	Total Calcium
Platelet Count	Creatinine
WBC with differential (5-part if available)	Albumin

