4.1. Inclusion Criteria

Patients must meet all of the following inclusion criteria to be eligible for enrollment into the study:

1. Histological or cytological diagnosis of advanced/metastatic solid tumor malignancy which has progressed on standard therapy or for which no standard therapy is available.
2. Measurable disease per RECIST v1.1.
3. Expansion cohort patients must have tumor accessible for sequential biopsy (core needle biopsy or excision preferred).
4. Age 18 years or older.
5. Eastern Cooperative Oncology Group (ECOG) performance status of 0 or 1 (see [Appendix 2](#)).
6. Adequate bone marrow function, defined as absolute neutrophil count (ANC) $\geq 1.5 \times 10^9/L$ ($\geq 1,500/\mu L$), platelet count $\geq 100 \times 10^9/L$ ($\geq 100,000/\mu L$), and hemoglobin $> 9.0 \text{ g/dL}$ ($> 5.6 \text{ mmol/L}$). Patients must be transfusion independent (ie, no blood product transfusions for a period of at least 14 days prior to study registration).
7. Adequate renal function, including serum creatinine $\leq 1.5 \times$ upper limit of normal (ULN) or estimated creatinine clearance $\geq 60 \text{ mL/min}$ as calculated using the method standard for the institution.
8. Adequate liver function, including: Total serum bilirubin $\leq 1.5 \times$ ULN (unless the patient has documented Gilbert syndrome), Aspartate and Alanine Aminotransferase (AST and ALT) $\leq 2.0 \times$ ULN, Alkaline phosphatase $\leq 2.5 \times$ ULN; ($\leq 5 \times$ ULN in case of bone metastasis).
9. Resolved acute effects of any prior therapy to baseline severity or Grade ≤ 1 CTCAE except for AEs not constituting a safety risk by investigator judgment.
10. Serum/urine pregnancy test (for females of childbearing potential) negative at screening and at the baseline visit (before the patient may receive the investigational product).
11. Male and female patients of childbearing potential must agree to use two (2) highly effective methods of contraception throughout the study and for 120 days after the last dose of assigned treatment.

Female patients who are not of childbearing potential (ie, meet at least one of the following criteria):

- Have undergone a documented hysterectomy and/or bilateral oophorectomy;
 - Have medically confirmed ovarian failure or;

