All measurable lesions up to a maximum of 2 lesions per organ, 5 lesions in total, representative of all involved organs, should be identified as target lesions at baseline. Target lesions should be selected on the basis of size (longest lesions) and suitability for accurate repeated measurements. Record the longest diameter for each lesion, except in the case of pathological lymph nodes for which the short axis should be recorded. The sum of the diameters (longest for non-nodal lesions, short axis for nodal lesions) for all target lesions at baseline will be the basis for comparison to assessments performed on study.

- If two target lesions coalesce the measurement of the coalesced mass is used. If a large target lesion splits, the sum of the parts is used.
- Measurements for target lesions that become small should continue to be recorded. If a target lesion becomes too small to measure, 0 mm should be recorded if the lesion is considered to have disappeared; otherwise a default value of 5 mm should be recorded.

NOTE: When nodal lesions decrease to <10 mm (normal), the actual measurement should still be recorded.

Non-target disease

All non-measurable disease is non-target. All measurable lesions not identified as target lesions are also included as non-target disease. Measurements are not required but rather assessments will be expressed as ABSENT, INDETERMINATE, PRESENT/NOT INCREASED, INCREASED. Multiple non-target lesions in one organ may be recorded as a single item on the case report form (eg, 'multiple enlarged pelvic lymph nodes' or 'multiple liver metastases').

OBJECTIVE RESPONSE STATUS AT EACH EVALUATION.

Disease sites must be assessed using the same technique as baseline, including consistent administration of contrast and timing of scanning. If a change needs to be made the case must be discussed with the radiologist to determine if substitution is possible. If not, subsequent objective statuses are indeterminate.

Target disease

- Complete Response (CR): Complete disappearance of all target lesions with the exception of nodal disease. All target nodes must decrease to normal size (short axis <10 mm). All target lesions must be assessed.
- Partial Response (PR): Greater than or equal to 30% decrease under baseline of the sum of diameters of all target measurable lesions. The short diameter is used in the sum for target nodes, while the longest diameter is used in the sum for all other target lesions. All target lesions must be assessed.

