- Stable: Does not qualify for CR, PR or Progression. All target lesions must be assessed. Stable can follow PR only in the rare case that the sum increases by less than 20% from the nadir, but enough that a previously documented 30% decrease no longer holds.
- Objective Progression (PD): 20% increase in the sum of diameters of target measurable lesions above the smallest sum observed (over baseline if no decrease in the sum is observed during therapy), with a minimum absolute increase of 5 mm.
- Indeterminate. Progression has not been documented; and
 - One or more target measurable lesions have not been assessed;
or
 - Assessment methods used were inconsistent with those used at baseline;
or
 - One or more target lesions cannot be measured accurately (eg, poorly visible unless due to being too small to measure);
or
 - One or more target lesions were excised or irradiated and have not reappeared or increased.

Non-target disease

- CR: Disappearance of all non-target lesions and normalization of tumor marker levels. All lymph nodes must be 'normal' in size (<10 mm short axis).
- Non-CR/Non-PD: Persistence of any non-target lesions and/or tumor marker level above the normal limits.

- PD: Unequivocal progression of pre-existing lesions. Generally the overall tumor burden must increase sufficiently to merit discontinuation of therapy. In the presence of SD or PR in target disease, progression due to unequivocal increase in non-target disease should be rare.
- Indeterminate: Progression has not been determined and one or more non-target sites were not assessed or assessment methods were inconsistent with those used at baseline.

New Lesions

The appearance of any new unequivocal malignant lesion indicates PD. If a new lesion is equivocal, for example due to its small size, continued assessment will clarify the etiology. If repeat assessments confirm the lesion, then progression should be recorded on the date of the initial assessment. A lesion identified in an area not previously scanned will be considered a new lesion.

Supplemental Investigations

- If CR determination depends on a residual lesion that decreased in size but did not disappear completely, it is recommended the residual lesion be investigated with biopsy or fine needle aspirate. If no disease is identified, objective status is CR.

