#### 6.2.2.2. Tumor Shrinkage

Tumor shrinkage will be summarized as the percent change from baseline in target lesions (sum of longest diameter for non-nodal lesion and short axis for nodal lesion) per time point. It will be derived as:

- $((\text{Sum of target lesions at week XX} - \text{sum of target lesions at baseline}) / \text{sum of target lesions at baseline}) \times 100$ .

The maximum reduction in target lesions from baseline will be derived across all the post-baseline assessments until documented disease progression, excluding assessments after start of subsequent anticancer therapy, as:

- Minimum of  $((\text{sum of target lesions at week XX} - \text{sum of target lesions at baseline}) / \text{sum of target lesions at baseline}) \times 100$ .

A waterfall plot of maximum percent reduction in the sum of longest diameter for non-nodal lesions and short axis for nodal lesions from baseline will be created. This plot will display the best percentage change from baseline in the sum of the diameter of all target lesions for each patient with measurable disease at baseline and at least one adequate post-baseline assessment.

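### If the mandatory week 9 biopsy hits a target lesion, that lesion leaves the follow-up sum but stays in the baseline sum, so tumour change is biased towards shrinkage

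*Protocol*

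**What the plan says.** **The biopsy.** Protocol Section 7.6: "Paired de novo tumor biopsies are mandatory for the patients enrolled in the expansion cohorts". Schedule of Activities, footnote 34: "A de novo biopsy will be required at study entry followed by a second biopsy at the time of the Week 9 scans". In dose escalation, biopsies are optional and unscheduled. Inclusion criterion 3 (Section 4.1) asks expansion patients for accessible tumour and names core needle and excision as the preferred techniques. It does not say whether the lesion may be a target.

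**The delisting rule.** Protocol Section 7.9: "a post-treatment biopsied lesion or a lesion that is radiated during the study should no longer count as a target lesion".

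**The comparator.** Appendix 1 takes the sum over all targets at baseline as the reference for on-study assessments. PR is a reduction of at least 30%, expressed as a "decrease under baseline of the sum of diameters of all target measurable lesions". SAP Section 6.2.2.2 summarises shrinkage as "percent change from baseline in target lesions (sum of longest diameter for non-nodal lesion and short axis for nodal lesion) per time point", divides by the baseline sum, and takes the minimum over assessments for the waterfall plot. Neither text recalculates the baseline or nadir after a lesion is delisted.

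**A second rule.** Appendix 1 sets target status to Indeterminate, unless progression is documented, when "One or more target measurable lesions have not been assessed", and also when a target was excised or irradiated and has not come back or grown.

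**The concern.** The protocol schedules a procedure that can change the set of lesions being summed midway through follow-up, yet its formulas compare sums as if the set were fixed. A patient whose disease has not changed can appear to have shrunk. Growth can be hidden at the first scan after the biopsy.

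The two rules for a disturbed target also disagree. Section 7.9 drops an irradiated lesion from the target set, while Appendix 1 keeps it as a target and calls the status Indeterminate. For an excised biopsy both rules apply, and they pull in opposite directions: one can create a response and the other can block confirmation of a real one.

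The expansion cohorts are meant to study anti-tumour activity and to support selection of the recommended Phase 2 dose, so a few misclassified patients could matter. Their size is not fixed in the documents. Assuming 10 to 20 patients, one misclassified responder moves the response rate by 1/10 = 10 to 1/20 = 5 percentage points.

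**Working it through.** The plan gives no figure on this point, so there is none to reproduce. The check applies the documents' own rules.

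**Inputs**
- At most 5 targets in total and 2 per organ; PR at -30% from baseline; progression (PD) at +20% over the smallest sum, with at least 5 mm absolute increase (Protocol Appendix 1).
- Scans at weeks 9, 15, 21 and so on (Protocol Section 7.9). PR confirmed by two determinations at least 4 weeks apart (SAP Section 6.2.2.1).
- *Post-treatment* in Section 7.9 is read as after the start of treatment. Protocol Section 9.5.1.4 uses the term in the same way for the second biopsy.
- Assumptions: the biopsied lesion is a target, and the week 9 scan precedes the biopsy (the order is not stated).

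**Step 1. Formula.** Let s be the dropped lesion's share of the baseline sum and x the proportional change in the retained lesions.
- Apparent change on the original baseline = (1 - s)(1 + x) - 1.
- Like-for-like change = x.
- With x = 0 the apparent change is -s, so the PR threshold is crossed when s is at least 0.30.

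**Step 2. k equal targets, s = 1/k**

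| k | Apparent change, x = 0 | x at which the apparent change is -30%: 0.70/(1 - 1/k) - 1 | x needed for +20% over a week 9 sum equal to baseline: 1.20/(1 - 1/k) - 1 |
|---|---|---|---|
| 2 | -50% | +40% | +140% |
| 3 | -33.3% | +5% | +80% |
| 4 | -25% | -6.7% | +60% |
| 5 | -20% | -12.5% | +50% |

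With two or three equal targets the drop alone passes -30%. With four or five, the retained lesions must also shrink by 6.7% or 12.5%. The artefact is present at weeks 15 and 21, which are 6 weeks apart, so it meets the 4-week confirmation rule.

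**Step 3. Unequal lesions (assumed sizes).** Targets of 40, 35 and 25 mm, all stable, with the 35 mm lesion dropped.
- Original baseline: (65 - 100)/100 = -35%, a PR.
- Like for like: (65 - 65)/65 = 0%, stable.

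If every lesion truly shrinks by 35%, the retained sum is 65 x 0.65 = 42.25 mm. That reads -57.75% on the original baseline and -35% like for like. Real responders are therefore exaggerated in the waterfall plot too.

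**Step 4. Progression.** Masking occurs while the nadir still contains the dropped lesion and the current sum does not. Take two assumed 40 mm targets with the week 9 sum equal to baseline (80 mm). One is dropped and the other grows to 48 mm by week 15.
- Original baseline: (48 - 80)/80 = -40%, a PR.
- Like for like: (48 - 40)/40 = +20% and +8 mm, which is PD.

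Once the week 15 sum is the smallest observed, later comparisons use the same lesions on both sides.

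**Step 5. The Indeterminate rule.** Take a genuine PR at week 9 with the target then excised.
- Weeks 15 and 21 are Indeterminate unless progression is documented, so there is no second PR determination.
- Best overall response falls to stable disease, since week 9 is past the 6-week minimum, and the patient counts as a non-responder.
- If Indeterminate is recorded as NE in the SAP, both visits are inadequate (SAP Section 5.2.11). PD at week 27 then follows two inadequate assessments, and PFS is censored at week 9 (SAP Table 3).

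**The case against.** The strongest reply has four parts.

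- **Redaction and the Study Manual.** Text after the quoted sentence in Section 7.9 is blacked out, and Section 7.6 refers to a Study Manual for collection details. A handling rule may sit there. This stands, and the point is limited to visible text. Section 7.6 cites the Manual for sampling days, preparation and shipping, however, and the visible SAP section that defines the calculation contains no adjustment.
- **Source of best overall response.** The SAP takes it from reported responses, not from its shrinkage formula. This also stands: only shrinkage and the waterfall plot follow directly. Investigators nevertheless report under Appendix 1, whose baseline is the same.
- **Choice of lesion.** Appendix 1 favours targets that can be measured repeatedly, which is a reason to biopsy elsewhere. It also makes every measurable lesion a target up to the caps, so a patient within the caps has no measurable non-target lesion to offer.
- **Importance.** Efficacy is secondary and descriptive, with no hypothesis test. This limits the severity but leaves the computed values wrong.

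A reader might go further in ways the documents do not support:
- *Every expansion patient is affected.* Only those whose biopsied lesion was a target are.
- *A sole target dropped gives -100% and hence a response.* No target is then left to sum, so this is not a PR.
- *Every later assessment becomes Indeterminate and a PR can never be confirmed.* The Indeterminate list names excision and irradiation, not needle biopsy. A needle-biopsied lesion can still be measured, and if it is delisted the remaining targets can satisfy the completeness condition.
- *Progression is hidden because the nadir rests on fewer lesions.* It is the reverse, as Step 4 shows. New lesions and unequivocal non-target progression still count as PD throughout.

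**Conclusion.** The concern holds in a conditional form. In expansion patients whose biopsied lesion was a target, applying Section 7.9 together with the unadjusted baseline sum biases percent change towards shrinkage by the dropped lesion's share: -50% to -20% for two to five equal lesions with no true change. A false PR is possible from a share of 30% upwards, or from a smaller share combined with some real shrinkage. Progression can be masked at the first scan after the biopsy.

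The waterfall plot is affected directly. Response rate, duration of response and PFS are affected if investigators use the same denominator. The false PR and the unconfirmed PR come from alternative readings, so they do not both apply to one assessment.

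The result rests on the visible text, on reading the baseline sum as unadjusted (no passage says in terms that it is kept after delisting), and on an unknown proportion of biopsies that hit targets. The dose-limiting toxicity endpoint and the maximum tolerated dose are not touched. The rules should be reconciled, because applied as written they give a wrong number.

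**What to change.** 1. **Protocol Sections 7.6 and 7.9 and footnote 34:** take the on-treatment biopsy from a lesion designated non-target at baseline whenever another measurable lesion exists. Add an explicit exception to the target-selection rule in Appendix 1, which otherwise makes that lesion a target.
2. **Protocol Section 7.9 and Appendix 1:** choose one rule for a target that is biopsied, excised or irradiated on study, and say whether needle biopsy falls under it.
3. **SAP Sections 6.2.2.1 and 6.2.2.2:** if a target is nevertheless delisted, compute the baseline and nadir sums on the retained lesions for all later time points. State the response status when no target remains, and flag these patients in the waterfall plot.

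In the example of Step 3 this returns 0% for the stable patient and -35% for the true responder. The cost is a few sentences in each document, and some patients will have one target lesion fewer. If the redacted text or the Study Manual already covers part of this, a cross-reference from the SAP would be enough for that part.

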8. ADVERSE EVENT REPORTING

8.1. Adverse Events

All observed or volunteered AEs regardless of treatment group or suspected causal relationship to the investigational product(s) will be reported as described in the following sections.

For all AEs, the investigator must pursue and obtain information adequate both to determine the outcome of the AE and to assess whether it meets the criteria for classification as a SAE requiring immediate notification to Pfizer or its designated representative. For all AEs, sufficient information should be obtained by the investigator to determine the causality of the AE. The investigator is required to assess causality. Follow-up by the investigator may be required until the event or its sequelae resolve or stabilize at a level acceptable to the investigator, and Pfizer concurs with that assessment.

As part of ongoing safety reviews conducted by the Sponsor, any non-serious AE that is determined by the Sponsor to be serious will be reported by the Sponsor as an SAE. To assist in the determination of case seriousness further information may be requested from the investigator to provide clarity and understanding of the event in the context of the clinical study.

